progression or toxicity. Ferumoxytol MRI (FeMRI) will be performed in the same day and sitting as the clinical MRI at baseline and 4 weeks after the last day of radiation timepoints. FeMRI may be performed independently (on a different day or different MRI setting) of the clinical MRI if there is suspected radiographic progression or to confirm radiographic progression. If there is suspected progression, subjects undergo a ferumoxytol steady state MRI and continue on pembrolizumab for one more cycle. The decision regarding continuation of pembrolizumab will be made by the principle investigator based on clinical findings that include (1) stable ECOG performance status with no more than 8mg of dexamethasone (or equivalent) a day; (2) absence of new or worsening symptoms not managed with steroids; and (3) absence of progressive tumor at critical anatomical sites (e.g., spinal cord compression) requiring urgent alternative medical intervention. Follow up clinical standard of care and ferumoxytol MRIs will be repeated to confirm persistent radiographic progression in 4 weeks. During this 4 week follow up period, subjects will be followed with a clinical exam weekly to monitor for clinical stability. If the 4 week follow up scan confirms progression (as defined in section 8.1), then pembrolizumab is discontinued and subject is evaluated for clinical indication of standard of care surgery or biopsy. Surgery or biopsy is performed only if 1) the lesion is deemed easily accessible 2) surgery is not expected to worsen neurological outcomes and 3) it is in the best clinical interest of the subject. The decision regarding surgery will be consensus based and when possible, will be made after each individual case has been presented at the OHSU multi-disciplinary brain tumor board. If histopathology confirms pseudoprogression or is inconclusive, the subject will continue on pembrolizumab every 3 weeks until further radiographic progression is suspected. If histopathology confirms progression, the subject will be removed from the study. Subjects with evidence of new lesions distant from the primary lesion/s (not present at entry to the study) in the CNS or systemically that fulfil criteria for progression by immune related response criteria (irRC)[1] will be taken off study drug, but will be followed with serial clinical standard of care MRI.

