A major challenge in managing and designing trials for brain tumors is determining tumor response to therapy, and then differentiating response from recurrence or treatment-related changes. After radiation, a large majority of these tumors can paradoxically increase in size due to an inflammatory response called ‘pseudoprogression’. The term pseudoprogression describes the phenomenon of subacute radio-chemotherapy treatment-related sequelae in patients with brain tumors that presents as increasing or new contrast enhancement on MRI [46, 47]. These patients stabilize or recover spontaneously, usually without any change in treatment. As cancer immunotherapeutics are being tested in clinical trials, pseudoprogression is increasingly becoming a growing challenge that needs to be addressed [48]. It is estimated that over 10 -12% of patients develop pseudoprogression before eventually showing a response that can be captured by conventional response assessment criteria after immunotherapy. Similarly, over 30% develop imaging changes that are consistent with pseudoprogression after radiation [49]. This number is significantly higher when immunotherapy is combined with standard of care radiation. Current standard of care imaging or response assessment criteria do not have the ability to differentiate this immune response from true progression at any given time point.

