Figure 4: Charts show survival of GBM patients according to $rCBV$ by using four cutoff values. Tumor $rCBV$ was measured by using ferumoxytol versus gadoteridol and gadoteridol with leakage correction (Gadoteridol LC). Kaplan-Meier survival curves show best survival prediction by using $rCBV$ values obtained with ferumoxytol ($P = .001$) when cutoff range is between 1.5 and 2.0, and the same result was achieved with gadoteridol LC with cutoff of 1.5. By using gadoteridol, survival prediction is similar but not statistically significant ($P = .079$) for all cutoff values. Colored areas indicate 95% CIs.

[figure not shown]

Figure 5: Brain imaging using ferumoxytol: (A) High resolution images showing intravascular iron. (B) Delayed enhancement 24 hours after ferumoxytol administration.

[figure not shown]
[figure not shown]
[figure not shown]

Figure 6. Comparison of steady-state-cerebral blood volume (SS-CBV) and dynamic susceptibility contrast (DSC)-CBV maps in a glioblastoma patient. (A) T1-weighted postgadoteridol scan describes the multifocal signal abnormalities. In corresponding slices, the SS-CBV (B) and DSC-CBV (C) maps show increased areas of CBV referring to highly vascular tumor areas. Note the mismatch between the most enhancing region (arrow) and the highest CBV values. Reprinted from Varallyay et al. (2013).

Another major problem with response assessment is the use of VEGF inhibitors like bevacizumab or corticosteroids. These agents can alter the neurovascular unit around the tumor and decrease contrast enhancement (pseudo-response) when measured by conventional response criteria. Bevacizumab has failed to show significant survival benefits but is frequently used as an anti-edema measure [67-69].

[figure not shown]
Our preliminary data suggests that use of bevacizumab may alter rCBV measurements in high grade gliomas. For the purpose of this study, a short course of up to 3 doses of bevacizumab may be allowed, when clinically indicated, as an anti-edema measure and will not be criteria for exclusion. Bevacizumab is preferred over steroids when studying immune-modulatory therapies, since use of steroids can potentially dampen the immune response and outcomes.

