Study MRI will be performed prior to the start of bevacizumab therapy whenever possible. Imaging data from subjects who require more than 3 doses of bevacizumab will be stratified and analyzed separately. A separate analysis of subjects based on their bevacizumab and steroid dose will be performed as part of the final analysis. Since this is not a randomized trial and the need for bevacizumab cannot be predicted prior to enrollment, stratification prior to enrollment is not possible and analysis will be performed post enrollment. Currently, the differences in the pathophysiology or response to bevacizumab in pseudoprogression resulting radiation or PD-1 inhibitors is not clear. This study will provide critical data that can provide insight to the use of bevacizumab as a steroid sparing agent to control the edema and mass effect. There are several ongoing studies evaluating the efficacy of the combination in brain tumors.

Delayed Ferumoxytol imaging: A biomarker for inflammation

In addition to uptake by the reticuloendothelial system, ferumoxytol and other iron oxide nanoparticles are taken up by tumor-associated macrophages [70-72] and brain microglia [73]. Delayed imaging of ferumoxytol in the CNS (figure 7) may therefore provide an important biomarker of inflammation and immune response in brain tumors [70, 74-76]. We have demonstrated that ferumoxytol iron oxide nanoparticles are taken up by phagocytic cells over hours to days after IV infusion (Figure 9). We are actively investigating the utility of ferumoxytol for imaging inflammation, assessing nanoparticle uptake into tumor-associated macrophages/microglia in inflammatory lesions (Figure 10). Our animal models suggest that the enhancement seen on T1 weighted images at >24 hr time point after ferumoxytol administration is believed to reflect the extent of local inflammation. This study will provide preliminary data regarding the significance of volume and extent of delayed ferumoxytol enhancement after immunotherapy.

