- **Confirmation of true progression:** For the purpose of this study, Histopathologic evidence of viable tumor cells in patients with persistent radiographic progression will be define to have confirmed true progression. True progression is confirmed by histopathology, Pembrolizumab will be stopped and patient swill be taken off-study.. Patients who refuse biopsy or biopsy is not deemed clinically necessary will be taken off study at persistent radiographic progression. However, they will be continued to be monitored with clinical MRI scan and until death.
- **Pseudoprogression (PsP):** for the purpose of this pilot study, PsP may be confirmed by imaging or by pathology.
 - PsP Imaging: stable or decrease in volume of enhancement at 4 weeks (\pm 5 days) after suspected radiographic progression.
 - PsP pathology: No viable tumor tissue is seen by histopathology evaluation on tissue obtained after confirmed radiographic progression by imaging.
- **Clinical progression:** Subjects may be removed from study if they experience symptomatic deterioration without radiographic evidence of disease progression.

Not evaluable (NE): Only relevant if any of the target lesions had additional interventions for clinical managements, patient is unable to get follow up scans or images are of poor quality.

Duration of Best Response: The duration of best response is measured from the time measurement criteria are met for SD, CR or PR (whichever is first recorded) until the first date that recurrent or PD is objectively documented (taking as reference for PD the smallest measurements recorded since the treatment started).

Progression free survival and overall survival will be calculated from the date of diagnosis to the date of confirmed progression or death, respectively. The date of diagnosis was used because the time between the date of diagnosis and the start of treatment or date of enrollment may vary due to subject variables or logistical issues based on radiation planning.

Systemic Lesions (only for Arm 1):

Measurements based on RECIST version 1.1 will be used to make a diagnosis of suspected systemic progression; it will be confirmed using irRC at follow-up.

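### The imaging rule for pseudoprogression has no condition on bevacizumab or steroids, so a treated true progression can enter the primary specificity analysis as pseudoprogression

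*Combined protocol and SAP*

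**What the plan says.** Section 8.1 states that "PsP may be confirmed by imaging or by pathology". The imaging criterion is "stable or decrease in volume of enhancement at 4 weeks" after suspected radiographic progression. It does not mention drugs given between the two scans.

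On VEGF inhibitors such as bevacizumab and on corticosteroids, Section 4.0 says: "These agents can alter the neurovascular unit around the tumor and decrease contrast enhancement (pseudo-response) when measured by conventional response criteria". On the index test it adds: "Our preliminary data suggests that use of bevacizumab may alter rCBV measurements in high grade gliomas". The same section allows up to 3 doses of bevacizumab against edema and prefers it to steroids. During the four-week wait, Section 2.0 lets pembrolizumab continue subject to, among other things, "stable ECOG performance status with no more than 8mg of dexamethasone (or equivalent) a day", and it accepts symptoms that steroids control.

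Sections 4.0 and 4.2 set out some handling. Study MRI is to precede bevacizumab where possible. Above the allowed course, "Imaging data from subjects who require more than 3 doses of bevacizumab will be stratified and analyzed separately". A further separate analysis by bevacizumab and steroid dose is promised for the final analysis.

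Section 10 bases specificity on patients whose pseudoprogression was determined by surgery or by follow-up clinical scan, with an rCBV cutoff of 1.75. It mentions neither drug, and it does not say which ferumoxytol scan supplies the rCBV value.

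**The concern.** The four-week scan decides who counts as pseudoprogression, and so who is in the specificity denominator. By the protocol's own account, bevacizumab and steroids can make enhancement stable or smaller without the tumour having been anything other than progressive. Suspected progression is also a time when edema treatment may be needed. A true progression treated in that window can meet the imaging definition as written.

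The effect depends on when rCBV was read. If it was read before the drug, a high value that is correct for tumour is scored as a false positive. If it was read after bevacizumab and was lowered by it, the index test and the reference label agree on the wrong answer, and nothing in the data shows it.

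The background text describes pseudoprogression differently: "These patients stabilize or recover spontaneously, usually without any change in treatment". The operational rule carries no trace of that qualification. A condition of this kind can be written: the complete-response definition in 8.1 asks that a residual abnormality hold or shrink in a patient no longer on treatment or steroids.

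**Working it through.** **1. The plan's own figures.** Exact (Clopper-Pearson) 95% intervals:
- Specificity 15/17 = 88.2% (63.6% to 98.5%). Section 10, Table 13 gives 88%, 64% to 99%.
- Sensitivity 22/26 = 84.6% (65.1% to 95.6%). Section 10, Table 12 gives 85%, 65% to 96%.

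Both reproduce.

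**2. How much rests on the imaging label.** Section 10 assumes 40% of 43 subjects have pseudoprogression: 0.40 × 43 = 17.2, taken as 17. It assumes 32 operated subjects, 26 of them with true progression on pathology, so at most 32 − 26 = 6 pseudoprogression cases can come from pathology. At least 17 − 6 = 11 of 17 (65%) then rest on imaging alone.

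**3. Effect of mislabelling.** Let m of the 17 labelled cases be treated true progressions, and let q be the probability that such a case reads below 1.75. Then

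expected specificity = [(17 − m) × 15/17 + m × q] / 17.

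- Case A, rCBV unaffected by treatment: q = 1 − 22/26 = 4/26 = 0.154.
- Case B, rCBV suppressed below the cutoff: q = 1.

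The change per mislabelled case is (q − 15/17)/17:
- A: (0.154 − 0.882)/17 = −4.3 points.
- B: (1 − 0.882)/17 = +0.7 points.

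The documents give no rate of bevacizumab or steroid use in the window, so m is an assumption, shown over a range:

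| m | Case A | Case B |
|---|---|---|
| 0 | 88.2% | 88.2% |
| 1 | 83.9% | 88.9% |
| 2 | 79.7% | 89.6% |
| 3 | 75.4% | 90.3% |
| 6 | 62.5% | 92.4% |

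For m = 3: A is (14 × 0.882 + 3 × 0.154)/17 = 12.81/17; B is (14 × 0.882 + 3)/17 = 15.35/17.

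**4. What case B hides.** If 15/17 is observed and 3 of the 15 low readings are suppressed true progressions, the result among genuine pseudoprogression is (15 − 3)/(17 − 3) = 12/14 = 85.7%.

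**The case against.** The best defence is that the plan knows about the problem. A reader might infer that it ignores the two drugs, or that the more-than-3-dose split is its only handling. The documents do not support either reading: Sections 4.0 and 4.2 also promise MRI before bevacizumab where possible and a separate analysis by bevacizumab and steroid dose. Section 8.1 places the ferumoxytol scan within 7 days of the clinical scan that raised suspicion, so a reading before bevacizumab is the evident intent. The not-evaluable category in 8.1 covers lesions that had additional interventions and could be read to apply. The trial is a descriptive pilot without a formal hypothesis.

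This limits the wording of the point but does not remove it:
- Scanning before bevacizumab protects the rCBV reading, not the four-week scan that assigns the label. It is not guaranteed, and nothing equivalent exists for steroids.
- The dose split counts total doses, so a subject with 1 to 3 doses inside the window stays in the main set.
- The dose-based analysis is by subject, has no method or time window, changes no label, and is missing from Section 10.
- The not-evaluable clause names neither drug. RANO is cited in 8.1 for persistent progression, not for the imaging pseudoprogression rule.

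Three other strong readings also fail. First, it is tempting to say that treated progressors *are* miscounted, but Section 4.0 says only that the drugs can reduce enhancement and that bevacizumab may alter rCBV. Second, a mislabelled subject need not be lost to sensitivity: under Section 7.4 such a subject continues until further persistent progression, which leads to surgical evaluation, so only that episode is necessarily lost. Third, recovery without a change in treatment is not part of the protocol's definition of pseudoprogression; the background says this is usual, not that it is required.

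**Conclusion.** The point holds as a gap in the reference standard of the primary objective. The imaging label is unconditional on two treatments that the protocol itself says can produce the finding the label depends on, and Section 10 puts every case so labelled into the specificity denominator.

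The size is conditional. It rests on the plan's illustrative 15/17 and 22/26, on treated progressors having the plan's sensitivity when rCBV is unaffected, and on an assumed number mislabelled. A reader might infer that specificity must be understated. That does not follow: each mislabelled case costs about 4.3 points if rCBV is unaffected and adds about 0.7 if it is suppressed, and the documents fix neither the rCBV effect nor the index scan. The figure of at least 11 of 17 holds for the planned counts and may differ in the data.

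**What to change.** Amend Section 8.1 and Section 10 before labels and rCBV are compared:

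1. Define the exposure window as the suspected-progression scan to the four-week scan.
2. In the primary specificity analysis, treat imaging-only pseudoprogression as indeterminate when bevacizumab was started or steroids were increased in that window, unless histology or later imaging free of those changes decides.
3. Name the index scan: the ferumoxytol MRI at suspected progression, done before any bevacizumab in that episode. State how an episode without such a scan is handled.
4. Report the all-comers result, with exposed episodes included, as a sensitivity analysis.

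The data are already collected, since Section 7.17.1 has all concomitant medication recorded. Because 8.1 changes, this is a protocol amendment needing review-committee and IRB approval under Section 13.5, not an analysis-plan edit alone. The statistical cost is a smaller specificity set: with three episodes set aside, for example, 12/14 = 85.7% with exact 95% CI 57% to 98%, against 15/17 with 64% to 99%. Setting aside edema-treated episodes may also select the remaining cases to some degree, which the all-comers result will show. Clinical use of either drug is unchanged.

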4.1 Trial Description

See section 2.0

4.2 Pharmaceutical and Therapeutic Background

The importance of intact immune surveillance in controlling outgrowth of neoplastic transformation has been known for decades. Accumulating evidence shows a correlation between tumor-infiltrating lymphocytes (TILs) in cancer tissue and favorable prognosis in various malignancies. In particular, the presence of CD8⁺ T-cells and the ratio of CD8⁺ effector T-cells / FoxP3⁺ regulatory T-cells seems to correlate with improved prognosis and long-term survival in many solid tumors.

The PD-1 receptor-ligand interaction is a major pathway hijacked by tumors to suppress immune control. The normal function of PD-1, expressed on the cell surface of activated T-cells under healthy conditions, is to down-modulate unwanted or excessive immune responses, including autoimmune reactions. PD-1 (encoded by the gene *Pdcd1*) is an Ig superfamily member related to CD28 and CTLA-4 which has been shown to negatively regulate antigen receptor signaling upon engagement of its ligands (PD-L1 and/or PD-L2). The structure of murine PD-1 has been resolved. PD-1 and family members are type I transmembrane glycoproteins containing an Ig Variable-type (V-type) domain responsible for ligand binding and a cytoplasmic tail which is responsible for the binding of signaling molecules. The cytoplasmic tail of PD-1 contains 2 tyrosine-based signaling motifs, an immunoreceptor tyrosine-based inhibition motif (ITIM) and an immunoreceptor tyrosine-based switch motif (ITSM). Following T-cell stimulation, PD-1 recruits the tyrosine phosphatases SHP-1 and SHP-2 to the ITSM motif within its cytoplasmic tail, leading to the dephosphorylation of effector molecules such as CD3 ζ , PKC θ and ZAP70 which are involved in the CD3 T-cell signaling cascade. The mechanism by which PD-1 down modulates T-cell responses is similar

to, but distinct from that of CTLA-4 as both molecules regulate an overlapping set of signaling proteins. PD-1 was shown to be expressed on activated lymphocytes including peripheral CD4⁺ and CD8⁺ T-cells, B-cells, T regs and Natural Killer cells. Expression has also been shown during thymic development on CD4-CD8- (double negative) T-cells as well as subsets of macrophages and dendritic cells. The ligands for PD-1 (PD-L1 and PD-L2) are constitutively expressed or can be induced in a variety of cell types, including non-hematopoietic tissues as well as in various tumors. Both ligands are type I transmembrane receptors containing both IgV- and IgC-like domains in the extracellular region and contain short cytoplasmic regions with no known signaling motifs. Binding of either PD-1 ligand to PD-1 inhibits T-cell activation triggered through the T-cell receptor.

PD-L1 is expressed at low levels on various non-hematopoietic tissues, most notably on vascular endothelium, whereas PD-L2 protein is only detectably expressed on antigen-presenting cells found in lymphoid tissue or chronic inflammatory environments. PD-L2 is thought to control immune T-cell activation in lymphoid organs, whereas PD-L1 serves to dampen unwarranted T-cell function in peripheral tissues. Although healthy organs express little (if any) PD-L1, a variety of cancers were demonstrated to express abundant levels of this T-cell inhibitor. PD-1 has been suggested to regulate tumor-specific T-cell expansion in subjects with melanoma (MEL). This suggests that the PD-1/PD-L1 pathway plays a critical role in tumor immune evasion and should be considered as an attractive target for therapeutic intervention.

Pembrolizumab is a potent and highly selective humanized monoclonal antibody (mAb) of the IgG4/kappa isotype designed to directly block the interaction between PD-1 and its ligands, PD-L1 and PD-L2. KeytrudaTM (pembrolizumab) has recently been approved in the United States for the treatment of subjects with advanced melanoma, 1st and 2nd line non-small cell lung carcinoma, head and neck cancer, and classical hodgkins lymphoma [6, 33].

Our preliminary data suggests that use of bevacizumab may alter rCBV measurements in high grade gliomas. For the purpose of this study, a short course of up to 3 doses of bevacizumab may be allowed, when clinically indicated, as an anti-edema measure and will not be criteria for exclusion. Bevacizumab is preferred over steroids when studying immune-modulatory therapies, since use of steroids can potentially dampen the immune response and outcomes. Study MRI will be performed prior to the start of bevacizumab therapy whenever possible. Imaging data from subjects who require more than 3 doses of bevacizumab will be stratified and analyzed separately. A separate analysis of subjects based on their avastin and steroid dose will be performed as part of the final analysis. Currently, the differences in the pathophysiology or response to bevacizumab in pseudoprogression resulting radiation or PD-1 inhibitors is not clear. This study will provide critical data that can provide insight to the use of bevacizumab as a steroid sparing agent to control the edema and mass effect. There are several ongoing studies in several tumor types (including brain metastases and primary brain tumors) evaluating the efficacy of the pembrolizumab and bevacizumab combination, however no study has a completed dataset. However, none of the studies are investigating the role of bevacizumab in pseudoprogression.

